The preliminary results of the tiotropium trial including asthmatic children from age of 1 year on (trial number: NCT01634113) [Vrijlandt et al. 2018], showed no differences in safety profiles between those receiving tiotropium 5 µg, those receiving tiotropium 2.5 ug, and those receiving placebo. No serious adverse events occurred in either of the tiotropium groups during the 12-week intervention period, whereas 3 of the 34 children receiving placebo experienced a serious adverse event (i.e. appendicitis, bronchopneumonia and exacerbation of asthma, viral upper respiratory infection), requiring hospital admission. Among other adverse events, there were no undesirable anticholinergic effects, or no differences in occurrence of adverse events between the intervention groups [Vrijlandt et al. 2018].

In addition, an earlier clinical trial on a short-acting non-selective anticholinergic agent, ipratropium bromide, in 25 children aged 5 to 15 years with severe acute asthma, found no significant differences in side effects between the study groups [Reisman et al. 1988]. Moreover, there is a recent report on tiotropium in cystic fibrosis, including 24 children aged 5 to 11 years, and 24 patients aged 12 years or older [Konstan et al. 2014]. Only two of these patients with cystic fibrosis experienced a serious adverse event, neither of which was considered drug-related [Konstan et al. 2014].

OBJECTIVE

The primary AIM of the study is

- 1) to find out the effect of intermittent tiotropium bromide and salbutamol as needed (TBS) versus intermittent fluticasone propionate and salbutamol as needed (FPS), or solely, salbutamol as needed (SA) on episode-free days in infants and toddlers with recurrent episodes of wheeze and/or shortness of breath.

Episode-free days are defined as those days during which there are no symptoms of wheeze and/or shortness of breath, no unscheduled medical visits for wheeze and/or shortness of breath, and no use of rescue or supplementary controller medications [Guilbert et al. 2006].

The secondary AIMS of the study are

to find out the effect of TBS versus FPS or SA treatment on

- 1) number of unscheduled physician visits for episodes of wheeze and/or shortness of breath,
- 2) need for bronchodilative medication,
and to evaluate
- 3) the safety of TBS versus FPS or SA treatment by paying attention to possible adverse events during treatment

in infants and toddlers with recurrent episodes of wheeze and/or shortness of breath.

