STATISTICAL POWER OF THE STUDY

The primary endpoint of the study is the proportion (%) of episode-free days in the TBS group, compared with the SA, after a 48-week intervention period. To ensure a 80% power to detect a 15% difference (corresponding to 1 day per week) in episode-free days between the treatment groups, at least 64 children per group were required, assuming a standard deviation of 27% for symptom-free days seen in a previous study [Bisgaard et al. 2006], and a possible drop-out percent of 20%. The calculation is based to reject the primary hypothesis with 5% significancy level.

STATISTICAL ANALYSIS PLAN

Normality of the distribution of continuous variables are to be evaluated by Shapiro-Wilk test. The overall difference between the treatment groups is to be evaluated by using either analysis of variance, Kruskal-Wallis, log-rank, chi-squared, or Fisher's exact tests. Pairwise analyses are to be performed by using Mann-Whitney U, chi-squared, or Fisher's exact tests. Bonferroni correction is to be applied in pairwise analyses by multiplying each P-value by 3. Influence of confounding factors on the primary outcome is to be assessed by conducting the two-way factorial analysis of variance. $P<0.05$ is to be considered statistically significant. All study participants are to be included in safety analyses, and those with diary data available are to be included in primary analysis. All analyses are to be performed as intention-to-treat. IBM SPSS Statistics (version 22.0; Armonk, NY, US) is to be used for all analyses.

RESEARCH METHODS AND MATERIAL, ETHICAL ISSUES

Inclusion criteria:

1. Children at the age of 6 to 35 months.
2. Two to four physician-confirmed episodes of wheeze and/or shortness of breath.
3. Parents/legal representatives with sufficient written and spoken skills in Finnish language

Exclusion criteria:

1. Birth before 36th week of gestation.
2. Suspected/diagnosed chronic parenchymal lung disease or a structural airway defect, or a history of thoracotomy with pulmonary resection.
3. A history of congenital or acquired heart disease, including any unstable or life-threatening cardiac arrhythmia.
4. Constipation with a need of regular medication, or a diagnosed/suspected structural defect in the gastrointestinal tract.
5. A history of malignancy, or other significant chronic disorder, disease, or defect.

Study population and study design

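### The 80% power is for one comparison at 5%, but the SAP multiplies every pairwise P-value by 3, leaving the primary TBS vs SA test with about 65% power

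*Combined protocol and SAP*

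**What the plan says.** Under *Statistical power of the study*, one comparison is named: "The primary endpoint of the study is the proportion (%) of episode-free days in the TBS group, compared with the SA" group after 48 weeks. The target is given as "To ensure a 80% power to detect a 15% difference (corresponding to 1 day per week) in episode-free days between the treatment groups", with the SD taken as 27%, drop-out as 20%, and at least 64 children per group as the result. On the significance level: "The calculation is based to reject the primary hypothesis with 5% significancy level". Sidedness is not stated. *Study population and study design* plans 195 children, 65 per group.

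Under *Statistical analysis plan*, an overall three-group test is followed by pairwise tests, with Mann-Whitney U as the option for a continuous outcome. Then: "Bonferroni correction is to be applied in pairwise analyses by multiplying each P-value by 3", with significance at P<0.05. Nothing exempts TBS vs SA, and nothing in the sample size allows for the correction.

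Under *Objective*, the primary aim sets TBS against both the fluticasone arm (FPS) and SA.

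**The concern.** The three sections imply three different families of comparisons: one in the power section, two in the primary aim and three in the SAP. TBS vs SA is a pairwise analysis, so as written its P-value is tripled. The stated power then describes a test the SAP does not carry out.

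Two things are at stake. First, the chance of detecting the effect the trial was designed to find is lower than stated. Second, the decision rule is open. A raw P-value for TBS vs SA between 0.0167 and 0.05 is positive by the power section and negative by the SAP, and nothing in the plan settles which applies.

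**Working it through.** **Inputs**

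- From the power section: difference δ = 15 points, SD σ = 27 points, power 80%, level 5%, drop-out 20%, 64 per group.
- From the design section: 65 per group randomised, so 65 × 0.8 = 52 evaluable.
- From the SAP: factor 3 on each pairwise P-value, so the per-comparison level is 0.05/3 = 0.0167.

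**Step 1: reproduce the plan's figure.** The normal formula for two means is

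n = 2(z₁₋α/₂ + z₁₋β)² σ²/δ²

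- Two-sided 5%: 2 × (1.960 + 0.842)² × 27²/15² = 50.9, so 51 evaluable. Then 51/0.8 = 63.75, so **64 per group**, an exact match.
- One-sided 5%: 41 evaluable, 52 after drop-out. No match.
- Two-sided 5%/3: z = 2.394, so 2 × (2.394 + 0.842)² × 27²/15² = 67.8, or 68 evaluable. Then 68/0.8 = 85. No match.

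The sample size is therefore a single two-sided 5% test with no allowance for the factor of 3.

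**Step 2: power at the level the SAP applies.** With 52 per group the standardised effect is (15/27) × √(52/2) = 2.833.

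- Normal approximation: Φ(2.833 − 1.960) = 80.9% at 0.05, and Φ(2.833 − 2.394) = 67.0% at 0.0167.
- The t-test (noncentral t) gives slightly lower values:

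| Evaluable per group | Power at 0.05 | Power at 0.0167 |
|---|---|---|
| 51 (64 less 20%) | 79.3% | 64.5% |
| 52 (65 less 20%) | 80.1% | **65.5%** |
| 65 (no drop-out) | 88.2% | 77.0% |

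**Step 3: what the correction costs.** With 52 per group, the difference detectable with 80% power by t-test rises from 15.0 to 17.4 points. Over a week that is 0.174 × 7 = 1.2 days, against a design target of about one day. Restoring 80% at 0.0167 needs 68 evaluable per group by the normal formula (85 randomised, 255 in all). By t-test it needs 70 (70/0.8 = 87.5, so 88 randomised, 264 in all).

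**Step 4: the planned rank test and the overall test.** Simulation with 52 per group and normal data (20,000 runs per setting, FPS mean at, midway above, or 15 points above SA):

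- Mann-Whitney with the ×3 rule: 62% to 63%.
- Also requiring a significant overall ANOVA: 61% to 62%.
- Mann-Whitney unadjusted: about 78%.
- Mann-Whitney unadjusted, but requiring a significant ANOVA first: 69% to 75%.

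**Step 5: the two-comparison family in the aim.** If TBS vs SA and TBS vs FPS were both primary, a factor of 2 would apply. At 0.025 with 52 per group, t-test power is 71%.

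**The case against.** The strongest objection is that 65% is a t-test figure, while the SAP would use Mann-Whitney U and the plan never assumes normality. The proportion of episode-free days is bounded and may be skewed, and a rank test can then do better. In beta-shaped illustrations with SD 27, 52 per group and the ×3 rule, power is about 65% for means of 45 vs 60, 71% for 55 vs 70, 81% for 60 vs 75, and 91% for 65 vs 80. This stands as a limit on the precision of the 65%. It does not support the stated 80%, because the plan gives neither a control mean nor a distribution, and its own 64 comes from the normal-theory formula.

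Second, the analysed number may exceed 52, since children who stop early can contribute the diary data already collected. That narrows the gap: power at 0.0167 is 73% with 60 evaluable and 77% with 65. It does not close it, and the 20% loss is the plan's own assumption.

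Third, the ×3 sentence follows the overall test and might be meant only for follow-up comparisons, with TBS vs SA standing apart at 5%. That may be the intention, but the wording covers each P-value in pairwise analyses.

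Fourth, the correction is conservative. It does not inflate the type I error or bias the estimate, and because the aim includes TBS vs FPS, some family-wise control serves a stated objective. Both points are fair. They argue for keeping a correction on the other comparisons, not for leaving the power statement as it is.

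**Conclusion.** The concern holds. The sample-size arithmetic is right for a single two-sided 5% test, but that is not the test the SAP prescribes for the primary comparison. Under the ×3 rule, the primary TBS vs SA comparison has about 65% power (64.5% to 67.0% by the standard formulas, 62% to 63% for the rank test on normal data). The risk of missing a true 15-point difference is about 35% rather than 20%.

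These figures rest on the plan's difference, SD and drop-out, on approximately normal data, and on a two-sided level, which is inferred because only that reproduces 64. The inconsistency itself depends on none of these except the reading of the text. It affects both the decision rule and the stated power of the primary endpoint, so it must be settled before the data are analysed.

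**What to change.** **Preferred.** State in the SAP that TBS vs SA on the proportion of episode-free days is the single primary comparison, tested at two-sided 5% without multiplication. Say also that it does not depend on a significant overall three-group test, since that requirement would lower the power again (Step 4). Make TBS vs FPS and FPS vs SA secondary and keep a correction for them. State the factor, and whether they are tested formally only if TBS vs SA is significant. Reword the primary aim under *Objective* so that it names the same single comparison.

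This restores the stated 80% with the planned 195 children (80.1% by t-test, about 78% by rank test on normal data). The price is that TBS vs FPS becomes explicitly secondary, although it was never powered separately.

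The edit is a few sentences, but it relaxes the threshold for the primary test in a trial that has been recruiting since April 2016. It should be dated, justified without reference to outcome data by arm, and assessed for notification as a substantial amendment.

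**Alternative.** Keep the ×3 rule for TBS vs SA and restate the power as about 65% under the plan's assumptions, or raise enrolment to 85 to 88 per group. Restating the power costs nothing but accepts the shortfall. Raising enrolment adds 60 to 69 children (255 − 195 and 264 − 195).

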195 consecutive patients will be recruited in the study. Before enrolment, respiratory infections should be treated, and significant thoracic anomalies should be excluded by taking a chest X-ray scan. Background information is questioned as follows: gestational stature, birth weight and length, ethnic background, allergy to food and inhaled allergens diagnosed or strongly suspected by a physician, respiratory symptoms, wheezing episodes confirmed by a physician, other significant illnesses or diagnoses, operations, medication, atopic diseases in family members, smoking and pets at home, moist or mould problems at home.

The study children will be randomized into three groups. One third of the patients (SA group, n=65) will receive inhaled salbutamol (Ventoline Evohaler® 0.1 mg/dose), i.e. rescue medication, to be used 0.2 mg 4 to 6 times a day as needed for wheeze and shortness of breath via a plastic spacer, Babyhaler®, during the whole study (i.e. SA group). One third of the patients (FPS group, n=65) will be randomized to receive fluticasone propionate (Flixotide Evohaler® 125 µg/dose), to be given 125 µg twice a day via Babyhaler®, beginning at the onset of an upper respiratory tract infection and continuing for 7 to 14 days as needed, and in addition, inhaled salbutamol (Ventoline Evohaler® 0.1 mg/dose), i.e. rescue medication, to be used 0.2 mg 4 to 6 times a day as needed for wheeze and shortness of breath via Babyhaler®, during the whole study. One third of the patients (TBS group, n=65) will be randomized to receive tiotropium bromide (Spiriva Respimat® 2.5 µg/dose), to be given 5 µg once a day via AeroChamber Plus®, beginning at the onset of an upper respiratory tract infection and continuing for 7 to 14 days as needed, and in addition, inhaled salbutamol (Ventoline Evohaler® 0.1 mg/dose), i.e. rescue medication, to be used 0.2 mg 4 to 6 times a day as needed for wheeze and shortness of breath via AeroChamber Plus®, during the whole study. The intervention will last for 48 weeks. The drugs and the plastic spacers will be supplied by the pharmacy of Helsinki University Hospital.

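### The factor-of-3 correction is not limited to efficacy, so it also makes a pairwise harm of tiotropium harder to establish (minor; fixed by a short SAP addition)

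*Combined protocol and SAP*

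**What the plan says.** The section STATISTICAL ANALYSIS PLAN first provides an overall comparison of the three groups, with chi-squared and Fisher's exact tests among the options. It continues: "Pairwise analyses are to be performed by using Mann-Whitney U, chi-squared, or Fisher's exact tests". Then: "Bonferroni correction is to be applied in pairwise analyses by multiplying each P-value by 3". A P-value below 0.05 "is to be considered statistically significant". None of these sentences is restricted to the primary outcome or to efficacy.

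The only rule specific to safety in that section is the analysis set: "All study participants are to be included in safety analyses". The third secondary aim in OBJECTIVE is to evaluate "the safety of TBS versus FPS or SA treatment by paying attention to possible adverse events during treatment".

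The section Study population and study design says which adverse events are recorded (those needing unscheduled medical attendance, and serious events needing admission) and sets 65 children per arm. The documents do not exempt safety from the correction, do not say that safety will be descriptive only, and do not plan a risk difference or confidence interval for adverse events.

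**The concern.** A familywise correction limits false claims that treatments differ. For efficacy that is the cautious direction. For adverse events it is not: the same correction makes a true harm more likely to be missed. The children are 6 to 35 months old, and the third secondary aim names exactly the contrasts to which the factor of 3 would apply.

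What is at stake is attribution. An excess on tiotropium could show in the overall test while the tiotropium contrasts themselves are reported as non-significant. With no planned estimate or interval, the reader would have counts and P-values only.

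This is separate from the effect of the correction on power for the primary endpoint. Resizing the trial for that endpoint would leave the safety rule as it is.

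**Working it through.** **Inputs.** Arm sizes are from Study population and study design: "One third of the patients (TBS group, n=65) will be randomized to receive tiotropium bromide" and "One third of the patients (SA group, n=65) will receive inhaled salbutamol". The factor of 3, the 0.05 threshold and Fisher's exact test are from the SAP. The documents give no expected adverse-event rates for this trial, so all rates below are assumptions.

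**The plan's own sample size.** STATISTICAL POWER OF THE STUDY gives 64 per group for the primary endpoint. With two-sided alpha 0.05, 80% power, a difference of 15 and an SD of 27: n = 2 × (1.960 + 0.842)² × 27² / 15² = 50.9, so 51. After 20% drop-out, 51 / 0.80 = 63.75, so 64. The figure reproduces. No power is stated for safety, so the arm size was not chosen for it.

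**Effective threshold.** Requiring 3P < 0.05 is the same as requiring P < 0.05 / 3 = 0.0167.

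**No events in the comparator.** For k of 65 against 0 of 65, the two-sided Fisher P is 2 × C(65,k) / C(130,k).
- k = 5: P = 0.058.
- k = 6 (9.2%): P = 0.0277; × 3 = 0.083.
- k = 7 (10.8%): P = 0.0132; × 3 = 0.040.

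**Fewest affected TBS children needed for significance, 65 v 65, Fisher.**

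| Events in comparator | Uncorrected | With factor of 3 |
|---|---|---|
| 0 | 6 | 7 |
| 1 | 8 | 10 |
| 2 | 10 | 11 |
| 5 | 14 | 16 |
| 10 | 21 | 23 |

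**Exact pairwise power.** This sums the product of the two binomial probabilities over all tables with more events on TBS and P < 0.05 (or 3P < 0.05).

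| Assumed rates, TBS v comparator | Uncorrected | With factor of 3 |
|---|---|---|
| 10% v 1% | 46% | 29% |
| 10% v 2% | 32% | 18% |
| 15% v 2% | 70% | 53% |
| 15% v 5% | 37% | 23% |
| 25% v 10% | 54% | 37% |
| 40% v 20% | 64% | 47% |

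The loss is about 14 to 17 percentage points throughout. At 5% v 0% it is smaller (11% to 4%) only because there is little power to lose.

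**Overall test, three-arm Fisher exact, 65 per arm, judged at 0.05.**
- TBS 6, SA 0, FPS 0: P = 0.0035. Each tiotropium contrast has raw P = 0.0277, or 0.083 after correction.
- TBS 6, SA 0, FPS 2: P = 0.029. TBS v SA is 0.083 after correction; TBS v FPS is 0.27 uncorrected.

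In both cases the overall test is significant and neither contrast named in the aim is. In the first, removing the factor of 3 makes both contrasts significant. In the second, it does so for TBS v SA only.

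**The case against.** The strongest reply is that the factor of 3 does not touch the overall test. With 6 events on TBS and 0 on SA, the overall exact P lies between 0.0035 and 0.044 for every FPS count from 0 to 6. If FPS is assumed to share the SA rate, the overall test has power of 71% for 10% v 1%, 84% for 15% v 2% and 48% for 15% v 5%, which is better than even the uncorrected pairwise test. A reader might infer from the correction rule that the corrected pairwise P-value would be the whole safety result, or that a clear imbalance would go unflagged. The documents do not support that: the overall test is planned in the same paragraph, and counts by arm would show where an excess lies. What remains is that the overall test does not formally name the arm, and its power depends on the FPS rate.

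A reader might also infer that the sponsor intends to read non-significance as safety. No sentence says so. Nor does the plan specify a pairwise safety test outright: the aim speaks of evaluating safety and the protocol of recording events. The point therefore rests on the SAP's general wording, which applies by default unless a sentence says otherwise.

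Two further replies have some force. The SAP also allows chi-squared tests: for 6 v 0, Pearson's test without continuity correction gives P = 0.0121, and × 3 = 0.036 is still significant. Expected event counts are 3 per arm, so Fisher is the likelier choice, but the plan does not fix it. And the low sensitivity is mainly due to arm size: uncorrected power is only 32% for 10% v 2%. The correction worsens this rather than causing it.

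Finally, the absence of planned estimates is a gap with or without the factor of 3. That is correct, and it is sensible to close both together.

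**Conclusion.** The point holds in a limited form and is minor. As written, the SAP requires raw P < 0.0167 for any pairwise adverse-event comparison. This makes it harder to attribute a harm to tiotropium in the two contrasts the safety aim names. The cost is one or two more affected children at the comparator counts tabulated, or about 14 to 17 points of pairwise power at most of the assumed rates.

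This rests on three assumptions: adverse events are compared pairwise, Fisher's exact test is used, and event rates are in the range shown. It affects a secondary aim, not the primary result, and the uncorrected overall test reduces its consequences.

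**What to change.** Add to the SAP, before adverse events are compared by arm:

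> The factor of 3 applies to efficacy comparisons only. Adverse events are reported per arm as the number and percentage of children affected, with the unadjusted risk difference and exact 95% confidence interval for TBS v SA and for TBS v FPS. A P-value of 0.05 or more is not taken as evidence of safety.

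This needs no extra children or data and changes no clinical procedure. The SAP names SPSS 22.0 for all analyses, so the statistician should confirm that it produces the chosen exact interval, or name another tool.

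The downside is that more chance imbalances may reach P < 0.05 in the safety tables. For a single event type this is modest, because Fisher's test is conservative at this size. With equal true rates, the uncorrected two-sided false-positive rate per comparison is 0.1% at a rate of 2%, 1.2% at 5% and 2.4% at 10%. Three comparisons on one event type therefore total at most about 3 × 2.4% = 7% at the highest of these rates, and under 4% at 5%. Testing many event types would add more, so such findings should be read with the interval and clinical review.
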